QALY's. The EQ-5D-5L will be assessed at randomization and 2, 3, 6 and 12 months from date of injury.

The Numeric Pain Rating Scale (NPRS) will be used to assess pain, where 0 implies no pain and 10 the worst possible pain measured at randomization, after 4 weeks of immobilization (when the immobilizing cast is replaced by a removable cast) and at 3, 6 and 12 months after date of injury.

Patient satisfaction will be measured by using the ICHOM Satisfaction with treatment results questionnaire (self designed by ICHOM) measured at randomization, after 4 weeks of immobilization (when the immobilizing cast is replaced by a removable cast) and at 3, 6 and 12 months after date of injury.

The adapted Dutch institute for Medical Technology Assessment (iMTA) Medical Consumption Questionnaire (iMCQ) and iMTA Productivity Cost Questionnaire (iPCQ) will be used to measure the amount of medical consumption, sick leave from work or lost productivity while at work and out-of pocket expenses due to a complete tear of the UCL and the questionnaires are adjusted for this study. A shortened version of the iPCQ including only questions about sick leave from work and lost productivity while at work is measured at baseline (at randomization). The full iMCQ and iPCQ will be measured at 2 (over the last 2 months), 3 (over the last month), 6 (over the last month, this will be multiplied by 3 for the cost effectiveness analysis), and 12 months (over the last month, this will be multiplied by 6 for the cost effectiveness analysis)) after injury. Data will also be cross-verified with data from the Electronic Patient Record (EPD). If the data appears distorted, the analysis will be conducted using various scenarios to ensure its accuracy.

CLINICIAN REPORTED OUTCOME MEASURES (CROM)

Functional outcomes will be assessed by the head investigator of the study site to improve the reliability of measurements as much as possible. Before and during the study, multiple meetings will be scheduled with local investigators to optimize study logistics. All measurements will be performed as described in the International Consortium for Health Outcomes Measurement International (ICHOM) standard outcome set for hand and wrist conditions. [11]

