7. STATISTICAL ANALYSIS

Data will be analyzed following intention-to-treat. Categorical variables will be presented as counts and percentages and continuous variables as median and interquartile ranges or mean and standard deviation based on the normality of the data. Differences in characteristics between groups will be compared using Fisher exact and Pearson's χ^2 tests for categorical variables, and Wilcoxon rank sum tests and unpaired t test will be used for continuous variables, where appropriate.

We will conduct a linear regression analysis for longitudinal data (i.e. a mixed model) in which we correct for relevant prognostic factors (age, sex, time between trauma and definite treatment, duration of hand therapy) and baseline scores of the Michigan Hand Questionnaire. In an additional step, we will correct for surgeons depending on the number of treating surgeons as well as the number of patients per treating surgeon. Results will be presented as differences between treatment and control with 95% Confidence intervals. The intervention will be labeled as non-inferior when the noninferiority margin of 8 lies outside the 95% CI of this difference, regarding the Michigan Hand Questionnaire measured at 6 months as our primary endpoint. In case missing data did not happen randomly, but was related to specific factors (e.g. more missing data for men than for women), we will correct for this. In an additional analysis, the absolute MHQ scores at 6 months will be adjusted for differences in baseline MHQ scores between the intervention and control group. The secondary outcomes: PSFS, EQ5D, ROM, Kapandji score, grip strength, pinch strength and pain will be analyzed in a similar manner. Differences between the two treatment groups in complication rates will be analyzed using the Chi-square test or the Fischer's Exact test (in case the expected incidence was less than five).

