If the null hypothesis in this study of nonoperative treatment not being clinically non-inferior at six months is not rejected, but indeed lower costs are associated with nonoperative treatment, then incremental cost-effectiveness ratios will be calculated as the extra savings per extra unit in MHQ score lost or the extra savings per additional QALY lost. If the null hypothesis is rejected, a costs analysis and an outcome analysis will be done as distinct partial economic evaluations. The time horizon will be 12 months. It is expected that effects and costs beyond 12 months are similar for both treatment strategies and that a lifetime time horizon is redundant.

Differences between groups will be assessed after correction for bias and using accelerate non-parametric bootstrapping to account for sampling variability, generating 5,000 replications. Results will be presented graphically by cost-effectiveness planes. Cost-effectiveness acceptability curves will be drawn for various levels of willingness-to-pay per QALY up to €50,000, because higher levels cannot be justified by the maximum observable disease burden in this target group of patients. A scenario analysis will be applied by excluding the productivity losses following sick leave. Subgroup analyses will be performed for patients with a paid job.

Missing cost and effect data will be imputed using multiple imputation according to the MICE algorithm developed by van Buuren. Rubin's rules will be used to pool the results from the different multiply imputed databases. [14]

Measurement and valuation of costs

We will gather data on the use of resources and the related costs regarding health care (e.g. medical specialist, hand-physiotherapist, treatment of complications), productivity losses (absenteeism (sick leave) and presenteeism (lowered efficiency while at work due to sick leave from work and lowered productivity while a work)) and out-of-pocket

V7 01-02-2024 25 of 30

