expenses by patient and family members (e.g. health related travel, extra private help). The Dutch iMTA Medical Consumption Questionnaire and iMTA Productivity Cost Questionnaire will be adapted to and prepared for the current study setting and disseminated to patients for completion after two, three, six and twelve months of follow up.(11,12) Case report forms or electronic patient dossiers will be used to gather inhospital data. Unit costing will be based on the most recent Dutch guideline on costing in health care research at the time of data analysis. Costing of productivity losses will adhere to the friction costs approach with the current friction period at time of analysis.(13) The base year for costing will be 2022, with unit costs price-indexed if originating from other calendar years.

Patient outcome analysis

Patient outcome analysis in addition to the clinical outcome measures relevant to patients (disability, pain, hand function) the economic evaluation will include the measurement of health status at baseline (within 2 weeks after trauma), at two, three, six and 12 months after injury with the EQ-5D-5L. [15] This questionnaire consists of 5 items, measuring (at 5-point scales) whether patients experience problems, and if so, to what extent with regard to mobility, self-care, daily activities, pain/complaints, and mood. Existing health valuation scoring algorithms (Dutch reference values available through www.euroqol.org) will be used to assign a health utility to each 5-items score pattern. The number of QALYs for each patient will subsequently be calculated by interpolation between successive measurement and determining the area under the curve for the follow-up period of 12 months.

V7 01-02-2024 26 of 30

ETHICAL CONSIDERATIONS

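### The economic analysis specifies no adjustment of the QALY difference for baseline EQ-5D-5L utility, which costs precision and leaves chance imbalance in the estimate

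*Protocol*

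**What the plan says.** Section 6.1.2 sets the schedule: "The EQ-5D-5L will be assessed at randomization and 2, 3, 6 and 12 months from date of injury". The Patient outcome analysis part of section 7 repeats it and places the first measurement within two weeks of the trauma: "the measurement of health status at baseline (within 2 weeks after trauma), at two, three, six and 12 months after injury with the EQ-5D-5L". QALYs are then obtained by joining the measured utilities and "determining the area under the curve for the follow-up period of 12 months", so the baseline utility is the first point of the curve.

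For the comparison of arms, the Cost effectiveness analysis part of section 7 says: "Differences between groups will be assessed after correction for bias and using accelerate non-parametric bootstrapping to account for sampling variability". It fixes 5,000 replications, multiple imputation by MICE with Rubin's rules, cost-effectiveness planes, and acceptability curves up to €50,000 per QALY. It names no covariate.

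The clinical part of section 7 does name covariates. The mixed model for the MHQ corrects for several prognostic factors "and baseline scores of the Michigan Hand Questionnaire". EQ-5D is listed among the secondary outcomes to be analysed in the same way.

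The economic part also says when a ratio is calculated: if non-inferiority is not shown and nonoperative treatment is cheaper. If non-inferiority is shown, costs and outcomes are analysed separately.

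**The concern.** Baseline utility acts on the QALY in two ways. It is part of the area itself, and it may predict the utilities that make up the rest. Section 3 specifies simple randomisation and section 4.4 requires 57 evaluable patients per arm, so some chance difference in baseline utility is to be expected. If the arms are compared on QALYs alone, part of the observed difference reflects where the patients started, and the interval is wider than it need be.

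The bootstrap sentence does not clearly close the gap. Its reference to bias is most plausibly a garbled description of the bias-corrected and accelerated bootstrap. That method corrects an interval and adjusts for no covariate.

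Read this way, the same EQ-5D data would be baseline-adjusted as a clinical secondary outcome and have no stated adjustment in the cost-utility analysis, where they form the effect measure.

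**Working it through.** The Protocol states no figure for the QALY comparison, so there is none to reproduce. Its 57 per arm does reproduce: margin 8, SD 15, one-sided 0.025 and 80% power give 57 per arm by the exact noncentral t calculation (power 0.806).

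**Inputs from the Protocol.** Measurements at baseline and 2, 3, 6 and 12 months; 57 per arm; ceiling €50,000 per QALY.

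**Assumptions, since the Protocol gives no such figures.** Utility SD 0.20 at every visit; the same slope of later on baseline utility at each follow-up visit (equal to the correlation when SDs are equal), taken as 0, 0.3 or 0.5. For the standard errors, the same correlation between every pair of visits.

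**Step 1: weights in the area.** The trapezoidal rule, with the curve starting at month 0, gives:
- baseline: (2/12)/2 = 1/12 = 0.083
- month 2: 0.125
- month 3: 0.167
- month 6: 0.375
- month 12: 0.250

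The later weights sum to 11/12. If the curve starts at two weeks instead, the baseline weight is 0.0625.

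**Step 2: expected chance imbalance.** SE of the baseline difference = 0.20 × √(2/57) = 0.0375. The 95% range is ±1.96 × 0.0375 = ±0.073.

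**Step 3: shift in the QALY difference.** Shift = imbalance × (1/12 + 11/12 × slope). For a one-SE imbalance:

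| Slope | Factor | QALY shift | At €50,000 per QALY |
|---|---|---|---|
| 0 | 0.083 | 0.0031 | €156 |
| 0.3 | 0.358 | 0.0134 | €671 |
| 0.5 | 0.542 | 0.0203 | €1,015 |

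Only the first row, 0.0031, is the direct effect of the baseline point. Everything above it comes from the assumed slope. At the edge of the 95% imbalance range the three shifts are 0.006, 0.026 and 0.040 QALY (€306, €1,316 and €1,989). Over SDs of 0.10 to 0.25 and slopes of 0 to 0.5, that edge runs from 0.003 to 0.050 QALY (€153 to €2,486).

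**Step 4: precision.** The SE of the unadjusted difference is SD(QALY) × √(2/57). Adjustment multiplies it by √(1 − r²), where r is the correlation between baseline utility and QALY:

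| Correlation between visits | SD(QALY) | r² | SE unadjusted | SE adjusted |
|---|---|---|---|---|
| 0 | 0.101 | 0.027 | 0.0189 | 0.0186 |
| 0.3 | 0.138 | 0.269 | 0.0259 | 0.0221 |
| 0.5 | 0.158 | 0.468 | 0.0297 | 0.0216 |

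The SE falls by about 1%, 15% and 27% respectively.

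**The case against.** The strongest reply is that the Protocol is silent. A reader might infer that it commits to an unadjusted comparison, but no sentence says so. The covariates of an economic comparison are often left to a later analysis plan, which is not at hand. There is also text pointing the other way. Section 6.1.2 introduces the area under the utility curve as the way to express the EQ-5D effect in QALYs, and section 7 analyses EQ-5D like the baseline-adjusted MHQ. Read together, the adjustment could extend to QALYs. The bootstrap sentence could even be taken as a promise to correct for bias in a wider sense.

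This stands as far as the wording goes: only the absence of a specified adjustment can be claimed. It does not remove the point. The economic part sets out the interpolation rule, replication count, imputation algorithm and willingness-to-pay ceiling in detail, yet gives baseline utility no role beyond the first point of the curve. The extension from section 6.1.2 is an inference, and the only baseline score that section 7 names is that of the MHQ.

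A second tempting inference is that the QALY result is biased, or that an imbalance passes into it in full. Neither holds. Under randomisation a chance imbalance averages to zero, and the bootstrap interval already includes this variability. The direct weight is 1/12. Because the baseline is taken soon after an acute injury, its link with utility at 6 to 12 months may be weak, which favours the lower rows of the tables. The euro figures also use the top of the willingness-to-pay range.

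Third, the cost-per-QALY ratio is calculated in only one branch of the plan. That is correct. In the other branch the QALY difference still feeds the outcome analysis, and also the planes and acceptability curves where these are drawn.

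**Conclusion.** The point holds as a low-cost improvement to a secondary analysis. The economic section specifies a QALY estimator with no baseline-utility term, and a better one is available from data already collected. What is lost is precision, together with conditional accuracy in the particular sample obtained; the estimate remains unbiased on average. With utility SD 0.20, 57 per arm and slopes of 0 to 0.5, a one-standard-error imbalance shifts the QALY difference by about 0.003 to 0.020, or €156 to €1,015 at the ceiling. The SD and slope are assumptions, and if the slope is near zero the gain is very small. The primary endpoint, the sample size and the non-inferiority conclusion are untouched. The ratio itself is affected only if non-inferiority is not shown and nonoperative treatment costs less.

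**What to change.** Add one sentence to the Cost effectiveness analysis part of section 7: the incremental QALY is estimated by regressing each patient's QALY on treatment arm and baseline EQ-5D-5L utility, within every bootstrap replicate and imputed dataset, and this adjusted difference is used in the outcome analysis, planes, acceptability curves and any ratio.

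Reword the bootstrap sentence to say bias-corrected and accelerated bootstrap if that is meant. If some other correction is intended, name it.

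One caveat: in both arms, section 5.1 lists the baseline surveys after randomisation, and section 6.2 makes the trial open. Knowledge of the allocation could colour the answers, so the baseline EQ-5D-5L should be completed before the allocation is disclosed.

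The cost is two sentences of text and an attention point for the sites on the order of the baseline steps. No extra data or patients are needed.

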7.1 Regulation statement

The study will be conducted according to the principles of the Declaration of Helsinki, version 64, October 2013 and in accordance with the Medical Research Involving Human Subjects Act (WMO) and the Algemene Verordening Gegevensbescherming (AVG).

7.2 Recruitment and consent

After the diagnosis complete UCL rupture has been confirmed by the hand surgeon and the patient meets the eligibility criteria, the patient will be informed about the study by the hand surgeon. When the patient is open to participation, the patient is informed that the coordinating investigator of the study site will take contact after a period of reflection (days) and when the patient agrees to participate, written informed consent is provided for participating in the study (randomization, treatment, analysis of data, completion of questionnaires, completion of follow-up), to reuse the data and to approach patients for follow-up studies.

7.3 Objection by minors or incapacitated subjects

Not applicable.

7.4 Compensation for injury

The sponsor/investigator has a liability insurance which is in accordance with article 7 of the WMO. The sponsor also has an insurance which is in accordance with the legal requirements in the Netherlands (Article 7 WMO). This insurance provides cover for damage to research subjects through injury or death caused by the study. The insurance applies to the damage that becomes apparent during the study or within 4 years after the end of the study. An exemption from the obligation to take out a WMO (Medical Research Involving Human Subjects Act) subject insurance has been granted by the Medical Ethics Review Committee (METC) based on Article 7, sixth paragraph, of the WMO. According to the METC, participating subjects face minimal or no risk as two common treatment methods are being compared. The liability insurance has been arranged in accordance with the provisions outlined in Article 7, ninth paragraph, of the WMO.

7.5 Incentives

Subjects will not receive compensation for participation in the study.

V7 01-02-2024 27 of 30

8. ADMINISTRATIVE ASPECTS, MONITORING AND PUBLICATION

8.1 Handling and storage of data and documents

Castor EDC will be used for storage of raw data and backup. All data is captured in Castor and is pseudonymized in such a way that the personal data can no longer be attributed to a specific data subject without the use of additional information. Such additional information is kept separately and it is subject to technical and organizational measures (e.g. information is not going outside of the study site that is including the patient) to ensure that the personal data are not attributed to an identified or identifiable individual. Additional data stored on the hard disk of IT system of the study site and protected by a password, only accessible by the coordinating investigator of the study site. Local storage of the data after the data collection phase (editing and analysis); csv. files exported from Castor EDC to analyze the data, protocols, contracts, documents and software of data editing are stored on the secure server of the Diakonessenhuis. All data will be retained for a maximum of 15 years (approval of the patient is covered by the patient informed consent form) concerning reproducibility. Depending on the end products in terms of reports and articles, the processed and used data will still be stored per product.

8.2 Monitoring and Quality Assurance

Monitoring will be performed in compliance with Good Clinical Practice (GCP) and rules and regulations as described by the Nederlandse Federatie van Universitair Medische Centra (NFU) in order to achieve high quality research and secure patient safety. Qualified and independent monitors will have access to the data and source documents of the trial.

8.3 Amendments

Amendments are changes made to the research after a favorable opinion by the accredited METC has been given. All amendments will be notified to the METC that gave a favorable opinion. Submission of an amendment includes a covering letter, an extract of the modified document and the new document.

8.4 Annual progress report

The sponsor/investigator will submit a summary of the progress of the trial to the accredited METC once a year. Information will be provided on the date of inclusion of the first subject, numbers of subjects included and numbers of subjects that have completed

V7 01-02-2024 28 of 30

the trial, serious adverse events/ serious adverse reactions, other problems, and amendments.

8.5 Temporary halt and (prematurely) end of study report

The investigator/sponsor will notify the accredited METC at the end of the study within a period of 8 weeks. The end of the study is defined as the last patient's last visit.

The sponsor will notify the METC immediately of a temporary halt of the study, including the reason of such an action. In case the study is ended prematurely, the sponsor will notify the accredited METC within 15 days, including the reasons for the premature termination.

Within one year after the end of the study, the investigator/sponsor will submit a final study report with the results of the study, including any publications/abstracts of the study, to the accredited METC.

8.6 Public disclosure and publication policy

The principal investigator ([name]) and coordinating investigator ([name]) are leading authors in this study. All investigators in the participating hospitals will be named collaborator in the assessment of this study. The principal investigator and study designers (further to determine) are allowed to present the results on research conferences.

